5.1. Study Assessments of Efficacy and Safety

Table 8: Schedule of assessment & study timepoints

	Baseline visit	2 Weeks	3 Months	6 Months	12 Months	18 Months	24 Months
Informed consent	Х						
Inclusion/Exclusion criteria	Х						
Medical history	Х						
Physical examination	Х						
Pregnancy test	Х						
Prior/Concomitant medications/Treatments	Х						
Facial photography (full face, 45° angle left and right, 90° angle left and right)	Х		Х	х	Х	X	X
Photographic assessment ¹ by blinded independent evaluator (II)				Х			Х
Global Aesthetic Improvement Scale (GAIS) ² by the subject			Х	х	Х	Χ	Х
Global Aesthetic Improvement Scale (GAIS) by on-site live independent evaluator (I)			х	x	х	X	X
Subject self-assessment for overall satisfaction	Х		Х	Х	Х	Χ	Х
Investigator self-assessment for injection satisfaction	Х						
Subject diary	Х	Х	Х	Х	Х	Х	Х
Administer study treatment ³	Х						
Safety assessment: Identify and Record AEs		Х	Х	Х	Х	Х	Х

The volume deficit is assessed using different aesthetic grading scales corresponding to the area of the face: the Mid-Face Volume Deficit Scale (see Table 4) is a 6 point photon numeral rating for classifying the severity mid-face volume deficit; the Jawline scale (see Table 5) is a 5 point photon numeral rating scale for classifying the severity of jawline ptosis; the Chin Retrusion Scale (see Table 6) is a 5 point photon numeral rating scale for classifying the severity of chin retrusion; the Temple Hollowing Scale (see Table 7) is a 5 point photon numeral rating scale for classifying the severity of temple hollowing.

² The Global Aesthetic Improvement Scale (GAIS) is a 5-point scale rating global aesthetic improvement in appearance, compared to pretreatment, The rating categories are classified as very much improved (1), much improved (2), slightly improved (3), no change (4), or worsened (5).

³ The administration of the study treatment, handover of the subject diary, and subject self-assessment for overall satisfaction could be done on a different date than the baseline/screening.

5.1.1. Day 1 - Baseline visit (incl. treatment administration)

During the screening/baseline visit, the following actions will be taken:

- Signing the Informed consent form.
- When signing the Informed Consent Form (ICF), the subject will be given the option to apply a black box over the eyes on the photographs that will be taken (if the independent evaluator will not be hindered to evaluate the treatment area(s) such as cheekbones and mid-face). In addition, the subject will be given the option to give consent to the use of the photos for the promotion of the study products.
- Screening according the inclusion and exclusion criteria.
- Analysing medical history.
- Physical examination: measuring the vital parameters (e.g. blood pressure, weight and height).
- Analysing prior or concomitant medications and/or treatments.
- A urine pregnancy test will be performed on potential childbearing women.
- Photographing the face at different angles (i.e., full face, 45°, and 90°).
- Subject will be given a questionnaire to indicate their overall satisfaction with the appearance of the area(s) of the face that will be treated (see appendix 5).
- Investigator will fill in the injection satisfaction questionnaire (see appendix 6).
- Treating the subject. The study doctor will inject one of the dermal fillers (MaiLi Volume or MaiLi Extreme) into the specific area(s) of the face. Which dermal filler you receive will depend on the area(s) of the face to be treated.
- Subject will be given a blank diary for the next period (Day 1 Week 2).

5.1.2. Week 2 - Safety Assessment Visit

- A safety assessment is performed including the recording of any adverse events.
- Subject will return the completed subject diary (Day 1 Week 2) and will be given a blank diary for the next period (Week 2 till Month 24).

5.1.3. Month 3 till Month 24 Visits

In the period from month 3 to month 24 of the study, the following actions will be carried out:

On month 3, 12 and 18:

- Photographing the face at different angles (i.e., full face, 45°, 90°). A black box will be placed over the eyes in the photograph if the subject has ticked this option when signing the Informed consent form.
- Subject will be given a questionnaire to indicate their overall satisfaction with the appearance of the treated area(s) of the face (see appendix 5).
- If the subject has completely filled in the subject diary or has lost it, he/she will receive another blank diary (Week 2 to Month 24).
- Subject and independent evaluator (I) will do a live assessment using the GAIS scale and the 'full face' photograph taken at the baseline visit (see appendix 7).
- A safety assessment is performed including the recording of any adverse events.

On month 6 and month 24:

- The same actions taken at the above timepoints.
- An assessment of the photographs will be made of any improvement in the face using appropriate assessment scale for the treated area(s), by a blinded independent evaluator (II) (here: blinding means that the evaluator does not know at what time in the study period the photograph were taken).

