2.1. Primary Objective

Evaluate the proportion of subjects with an improvement (score of 3 and above) at 6 months in the Global Aesthetic Improvement Scale (GAIS) with assessments of:

- MaiLi Volume as a treatment for mid-face volume deficit and temporal hollowing.
- MaiLi Extreme as a treatment for mid-face volume deficit, jawline ptosis and chin retrusion.

as determined by an on-site live independent evaluator.

Evaluate safety through the collection of all adverse events, inclusive of Serious Adverse Events (SAE), unanticipated problems, and Unanticipated Adverse Device Effects (UADE), experienced in the post-treatment follow-up period.

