2.2. Secondary Objectives

Evaluate:

- The proportion of subjects with an improvement (score of 3 and above) in Global Aesthetic Improvement Scale (GAIS) assessments of the i) mid-face and ii) jawline and iii) chin area and iv) temple at 3, 12, 18 and 24 months by an on-site live independent evaluator.
- The proportion of subjects with an improvement (score of 3 and above) in Global Aesthetic Improvement Scale (GAIS) assessments of the i) mid-face and ii) jawline iii) chin area and iv) temple at 3, 6, 12, 18 and 24 months by the subject.
- The proportion of subjects exhibiting an improvement of ≥ 1 point from baseline on the mid-face volume deficit scale at 3, 6, 12, 18 and 24 months as rated by a blinded independent evaluator.

or

The proportion of subjects exhibiting an improvement of ≥ 1 point from baseline on the scale for the assessment of jawline sagging at 3, 6, 12, 18 and 24 months as rated by a blinded independent evaluator.

or

The proportion of subjects exhibiting an improvement of ≥ 1 point from baseline on the chin retrusion assessment scale at 3, 6, 12, 18 and 24 months as rated by a blinded independent evaluator.

or

The proportion of subjects exhibiting an improvement of ≥ 1 point from baseline on the temporal hollowing assessment scale at 3, 6, 12, 18 and 24 months as rated by a blinded independent evaluator.

Subject and Investigator treatment satisfaction will be assessed by questionnaire.

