The content of the syringe is sterile until opening. The external surface of the syringe is not sterile and should not be used in a controlled environment such as an operation room. If needed, the surface of the syringe must be cleaned up in respect of the aseptic techniques in place.

Once the treatment is done, a safety assessment will be conducted and the investigator will do another photographic assessment of the subject. The investigator will complete the electronic case report form (eCRF) of the subject before giving instructions for the next follow-up appointment. The subject will be given a diary card to bring home and record any adverse reactions they experience. The subject will then bring back the diary card on their first follow-up appointment 2 weeks after the treatment. The diary card will be reviewed and documented down by the investigator.

For the subsequent follow-up visits (i.e. 3 months, 6 months, 12 months, 18 months, and 24 months after the treatment), the subject will be given a questionnaire to assess their overall satisfaction with the results of their treatment (see appendix 5).

During the study, two independent evaluators will be involved:

• An on site live independent evaluator (I) (one for each site (4)) will be responsible for

- conducting the live Global Aesthetic Improvement Scale (GAIS) assessment during the subject's scheduled visits at 3, 6, 12, 18, and 24 months (see appendix 7). This assessment will be done in comparison to the face of the subject (at the time of the visit) and the 'full face' photograph taken at the baseline visit.
- A blinded independent evaluator (II) (one per country (2)) will be responsible for the remote assessment of the photographs using the different aesthetic grading scales (namely: Allergan Mid-Face Volume Deficit Scale, Merz Aesthetics scale for Jawline, Allergan Chin Retrusion Scale, and/or Allergan Temple Hollowing Scale). This evaluator will do the assessment of the photographs of all performed visits at month 6 (to generate the data for the interim 6 months report) and 24 (for the final report) of the follow-up period.

Photographs will be taken at each visit, and assessed by a blinded independent evaluator at 6 months and 24 months.

All data collected for the study will be kept in a secure place and is only accessible to the study's team members.

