8. SAMPLE SIZE AND STATISTICAL METHODS

8.1. Determination of Sample Size

The study population will include all subjects who are enrolled, and the entire study population will be included in statistical analysis.

Average Efficacy=85% Lower bound of 95% Confidence Interval (CI) =65% Clinical Margin=-20% Alpha=5% Power= 80% (Beta =0.20)

Considering 20% dropout rate, a total of 168 subjects (42 per site; a minimum of 36 per site respectively), to meet a completed study size requirement of 140, will be recruited.

- Mild to significant facial volume deficit (mid-face area) (n=60 (50), MaiLi Volume 30 (25) subjects and MaiLi Extreme 30 (25) subjects)
- Mild to moderate jawline ptosis (n=36 (30), MaiLi Extreme)
- Minimal to severe chin retrusion (n=36 (30), MaiLi Extreme)
- Minimal to severe temporal hollowing (n=36 (30), MaiLi Volume)

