Q5J I feel more attractive after the treatment of my jawline						
Q6J I look younger after treatment of my jawline						
Q7J The treatment of my jawline looks natural						
Chin	Totally agree	Agree	Somewhat agree	Somewhat disagree	Disagree	Totally disagree
Q1C I am satisfied with the appearance of my chin						
Q2C I am satisfied with the outline/contour of my chin						

Table 9 "Subject's Overall Satisfaction Questionnaire": These two questionnaires will be completed by the subject during the course of the study to measure the overall satisfaction of the subject during the study duration. Only the table that applies to the subject will be filled in.

Q3C The retrusion of my chin has

Q4C I feel more attractive after

Q6C The treatment of my chin

the treatment of my chin Q5C I look younger after

treatment of my chin

been reduced

looks natural

	Very satisfied	Satisfied	Neither satisfied nor dissatisfied	Dissatisfied	Very dissatisfied
Ease of injection					
Mouldability					
Ease of product positioning					
Immediate result					
Result after massage					

Table 10 "Investigator's Satisfaction Questionnaire": This questionnaire will be completed by the investigator shortly after administration of the study treatment. The purpose of this questionnaire is to obtain feedback on the satisfaction of using the MaiLi Volume or Extreme product during the treatment procedure.

	Rating	Description	
1	Worse	The appearance is worse than the original condition	
2	No change	The appearance is essentially the same as the original condition	
3	Improved	Improvement in appearance from the initial condition but re- treatment is indicated	
4	Much improved	Marked improvement in appearance but not completely optimal	
5	Very much improved	Excellent corrective results	

Table 11 "Global Aesthetic Improvement Scale (GAIS) Questionnaire": This questionnaire will be completed by the on-site level independent evaluator at the time of the subjects' scheduled visits (i.e. month 3, 6, 12, 18, and 24). The assessment scale will be done using the full face picture (taken at the baseline/screening visit (incl. treatment administration)) and the face of the subject at the time of the visit. This questionnaire is designed to measure the level of improvement in facial volume restoration and recontouring.

JCAD AESTHETIC COMPLICATIONS GUIDELINES

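### The protocol does not ensure that the primary month-6 GAIS is rated without knowledge of the subject's own GAIS and satisfaction answers

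*Protocol*

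**What the plan says.** - **Primary endpoint (Protocol 2.1, repeated in 8.2).** The proportion of subjects with a GAIS score of 3 or more at 6 months, "as determined by an on-site live independent evaluator".
- **Subject's GAIS (Protocol 2.2).** A secondary endpoint with the same threshold, for each area, the list ending "iv) temple at 3, 6, 12, 18 and 24 months by the subject". Month 6 is therefore shared with the primary.
- **Evaluator's task (Protocol section 5).** The live evaluator is responsible for "conducting the live Global Aesthetic Improvement Scale (GAIS) assessment during the subject's scheduled visits". The basis is the live face against the baseline full-face photograph: "This assessment will be done in comparison to the face of the subject (at the time of the visit".
- **Visit procedure (Protocol 5.1.3).** For months 3, 12 and 18: "Subject and independent evaluator (I) will do a live assessment using the GAIS scale", with the baseline full-face photograph and a reference to Appendix 7. Months 6 and 24 repeat these actions. The subject's satisfaction questionnaire is another item in the same list.
- **GAIS form (Appendix 7, Table 11).** The caption says the "questionnaire will be completed by the on-site level independent evaluator at the time of" the scheduled visits. No GAIS form for the subject appears.
- **Schedule (Table 8).** The two GAIS ratings have separate rows at the same visits. Footnote 2, attached to the subject's row, numbers the scale from 1 = very much improved to 5 = worsened. Tables 3 and 11 number it from 1 = worse to 5 = very much improved.

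**The concern.** The two GAIS ratings are meant to be different evidence: one from an independent rater, one from the treated person. The protocol describes them as one activity, at one visit, with one photograph and one form, and says nothing about keeping the first from being influenced by the second.

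The study is open-label, so evaluator (I) already knows that the subject was treated. Separation from the subject's own verdict is one of the few safeguards still available for the primary rating, and it is not used. If the subject's opinion does reach the evaluator before the score is recorded, the primary proportion could move towards that opinion, and the two GAIS endpoints would agree more than two separately made ratings would. No later analysis could undo this, because the recorded scores would carry no trace of it. For the same reason it is not a matter to be left to a statistical analysis plan: visit procedure, masking and forms are fixed in the protocol.

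**Working it through.** The protocol gives no figure on this point, so the check is a comparison of its passages.

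1. **Are the two ratings made at the same visit?** Yes. Section 2.2 and Table 8 put the subject's GAIS at months 3, 6, 12, 18 and 24. Section 5 and Table 8 put the evaluator's GAIS at the same five visits.

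2. **Is an order set?** No. Section 5.1.3 lists actions without saying that the list is a sequence, and the protocol's lists are not reliably chronological. Section 5.1.1 lists the investigator's injection questionnaire before the treatment itself, while the caption of Table 10 (Appendix 6) has it completed shortly after administration.

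3. **Is separation or masking required?** No. Section 5 names the face and the photograph as the basis of the evaluator's rating. It does not say that the subject's answers are withheld. The same section 5.1.3 does define blinding for evaluator (II), who must not know when a photograph was taken. The protocol thus states a masking rule for a secondary rating and none for the primary one.

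4. **Is there a separate instrument for the subject?** No. Section 5.1.3 sends both raters to Appendix 7, and Table 11 there is assigned to the evaluator only. How the subject's score is recorded, and by whom, is left open.

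5. **Is the subject's scale direction consistent?** No. Success is a score of 3 or more.
   - In Tables 3 and 11, scores 3, 4 and 5 are improved, much improved and very much improved.
   - In footnote 2 of Table 8, scores 3, 4 and 5 are slightly improved, no change and worsened.
   
   A subject who used the footnote's numbering would have the two best grades counted as failures and the two worst as successes. A subject form with a stated direction is therefore needed in any case.

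6. **How sensitive is the endpoint to single ratings?** The threshold lies between grade 2 (no change) and grade 3 (improved, with retreatment indicated), so a one-grade shift at that point turns a failure into a success. Section 8.1 gives completed group sizes of 25 (mid-face, each product) and 30 (jawline, chin, temple).
   - One changed rating: 1/30 = 3.3 points; 1/25 = 4.0 points.
   - The 20-point distance between the expected 85% and the 65% bound: 0.20 × 30 = 6 ratings; 0.20 × 25 = 5 ratings.
   
   This shows only how few ratings matter. It is not an estimate of how many would change.

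**The case against.** The strongest reply is that nothing says the raters confer. One sentence may name two raters who work apart. Table 8 gives them separate rows, section 5 defines the evaluator's rating without the subject's opinion, and one template in Appendix 7 can be copied for each. Section 7.1.1 also promises training and other standardisation across sites. All of this stands, and it limits the point to what the protocol fails to ensure. It does not close the gap: no text requires separation, and the general promise of standardisation does not mention it.

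Four stronger readings are tempting and are not supported:

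- *That the evaluator's rating is not independent, or that the evaluator hears or records the subject's score.* No passage says so. Only the shared visit is certain; one joint session is a natural reading of 5.1.3 but not a stated fact.
- *That the rating follows the satisfaction questionnaire.* This rests on list order, which step 2 of the working shows to be unreliable.
- *That the primary result is inflated by a calculable amount.* The documents give no carry-over rate, and a dissatisfied subject could pull a rating down as easily as a satisfied one could pull it up. Nor do the secondary endpoints lose all value as support: evaluator (II) rates month-6 photographs remotely, blinded to time point.
- *That a treatment group could be rated mostly by one person*, because there is one live evaluator per site and section 8.1 fixes only site totals ("a total of 168 subjects (42 per site; a minimum of 36 per site respectively"). The protocol does not say how the areas will be spread over sites. Any such clustering is a separate question with a different remedy and no part of this point.

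**Conclusion.** The point holds as a gap in protection. The protocol places the primary rating and the subject's rating of the same outcome at one visit, in one instruction, with one form assigned to the evaluator, and does not require the primary rating to be made unaware of the subject's answers. It reaches every primary rating at month 6 and the evaluator's secondary GAIS ratings at the other four visits. The size and direction of any bias are unknown, and no number should be attached to it. The conclusion assumes only that sites follow the protocol as written and that no other trial document, not shown here, already imposes the separation. The reversed numbering in footnote 2 of Table 8 is a plain contradiction and needs no assumption.

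**What to change.** - **Section 5.1.3, all GAIS visits.** State that evaluator (I) rates and records GAIS first, from the live face and the baseline full-face photograph alone, unaware of the subject's GAIS and satisfaction answers at that visit. The subject then completes GAIS separately, without being shown the evaluator's score.
- **Appendix 7.** Add a GAIS form for the subject with the direction of Tables 3 and 11 printed on it (1 = worse to 5 = very much improved). Keep Table 11 as the evaluator's form.
- **Table 8, footnote 2.** Align the numbering and labels with Tables 3 and 11.

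The cost is a set visit order and one extra page, with no added visit, staff or sample size. The change does not remove the evaluator's knowledge that the subject was treated, which is inherent in the open-label design.

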5.1.5. End of Study (EoS)/ Premature Discontinuation Visit

- The subjects will come to the Investigator's office.
- They will bring back their completed subject diary.
- Collection of the eventual adverse events and concomitant treatments.

5.1.6. Unscheduled/ Rescue treatment Visit

Subjects should receive prompt medical attention. Evaluation by an appropriate medical practitioner specialist could be necessary in case of an intravascular injection that should occur. In case of adverse device effect affecting subject well-being, the investigator is authorized to prescribe to the subject a rescue treatment. The adverse event (AE) will be recorded in the subject's electronic Case Report Form (eCRF) and source document, including details on rescue medication.

6 SAFETY MEASUREMENTS

6.1. Definitions

6.1.1. Investigational Medical Device

An investigational medical device that is being assessed in a clinical investigation. This definition includes medical devices already on the market that are being evaluated for new intended uses, new populations, new materials, and/or design changes. In this protocol, the terms "investigational medical device" and "investigational device" are used interchangeably.

6.1.2. Adverse event (AE)

An AE is defined as any untoward medical occurrence, unintended disease or injury, or untoward clinical sign (including abnormal laboratory findings) in subjects, users or other persons, whether or not related to the investigational medical device and whether anticipated or unanticipated

- Note 1 to entry: This definition includes events related to the investigational medical device or the comparator.
- Note 2 to entry: This definition includes events related to the procedures involved.
- Notes 3 to entry: For users or other persons, this definition is restricted to events related to the use of investigational medical devices or comparators.

6.1.3. Adverse device effect (ADE)

An ADE is defined as an adverse event related to the use of an investigational medical device.

- Note 1 to entry: This definition includes adverse events resulting from insufficient or inadequate instructions for use, deployment, implantation, installation, or operation, or any malfunction of the investigational medical device.
- Note 2 to entry: This definition includes any event resulting from use error or from intentional misuse of the investigational medical device.
- Note 3 to entry: This includes comparator if the comparator is a medical device.

6.1.4. Serious adverse event (SAE)

A SAE that led to any of the following:

- Death
- Serious deterioration in the health of the subject, users, or other persons as defined by one or more of the following:
 - Life-threatening illness or injury, or
 - A permanent impairment of a body structure or a body function including chronic diseases, or
 - In-patient or prolonged hospitalization, or
 - Medical or surgical intervention to prevent life-threatening illness or injury, or permanent impairment to a body structure or a function,
- Fetal distress, fetal death, a congenital abnormality, or birth defect including physical or mental impairment.

NOTE 1 to entry: Planned hospitalization for a pre-existing condition, or a procedure required by the CIP, without serious deterioration in health, is not considered an SAE.

